### 8.1.2 28-joint evaluation for determination of Disease Activity Score-28 (C-reactive Protein)

The following 28 joints will be used for calculation of the DAS28(CRP).

- Shoulder joints (x2)
- Elbow joints (x2)
- Wrist joints (x2)
- MCP joints of the hands (x10)
- PIP joints of the hands (x8) and IP joints of the thumbs (x2)
- Knee joints (x2)

Joints will be categorized and handled in the same way as for the 76/78-joint evaluation (Section 8.1.1).

### 8.1.3 Patient's Global Assessment of Disease Activity

Subjects will complete the PGADA using a visual analog scale (VAS) where 0mm is “very good, no symptoms” and 100mm is “very poor, severe symptoms”. The subject should be asked to consider both joint and skin components in their response to this question.

### 8.1.4 Physician's Global Assessment of Disease Activity

The Investigator will complete the PhGADA by assessing the overall status of the subject with respect to their PsA signs and symptoms and functional capacity (considering both joint and skin components) using a VAS where 0mm is “very good, asymptomatic and no limitation of normal activities” and 100mm is “very poor, very severe symptoms which are intolerable and inability to carry out all normal activities”.

### 8.1.5 Patient's Assessment of Arthritis Pain

The PtAAP VAS is part of the ACR core set of measures in arthritis (Felson et al, 1993). Subjects will assess their arthritis pain using a VAS where 0mm is “no pain” and 100mm is “most severe pain”.

### 8.1.6 Health Assessment Questionnaire-Disability Index Score

[figure not shown]
The HAQ-DI contains 20 items divided into 8 domains that measure: dressing and grooming (2 items), arising (2 items), eating (3 items), walking (2 items), hygiene (3 items), reach (2 items), grip (3 items), and common daily activities (3 items). Subjects are required to indicate the degree of difficulty they have experienced in each domain in the past week on a 4-point scale that ranges from 0 (without difficulty) to 3 (unable to do).

Each category is given a score by taking the maximum score of each question (the question in each category with the highest score is the score for that category).

If the maximum score equals 0 or 1, but a device related to that category is used, or help from another person is provided for the category, then the category score is increased to 2. If the category score is already a 2, and a device related to that category is used, or help from another person is provided for the category, the score for that category remains 2.

The association of each aid and device with the category scores is shown in Table 8-3. The use of devices classed as ‘Other’ will not be accounted for in the final score.

**Table 8-3: Aid or device associated with health assessment questionnaire-disability index domain**

If all questions within a given category are unanswered, no score will be provided for that category (this rule applies even if aids and devices are non-missing).

The HAQ-DI score (range 0 to 3) will be calculated by dividing the sum of the highest score in each category (0 to 24) by the number of categories with at least 1 question answered. If fewer than 6 categories have responses, no HAQ-DI score will be calculated. A lower HAQ-DI score indicates an improvement in function.

### 8.1.7 High-sensitivity C-reactive protein levels

Note that high sensitivity C-reactive protein is referred to as CRP throughout this SAP. CRP levels will be analyzed by the central laboratory.

Due to a change in laboratory vendor between PA0008 and PA0009, CRP values from the PA0009 laboratory have been calibrated to match those from the PA0008 laboratory, and these values will be used for all CRP summaries and listings.

In PA0008, the LLOQ was 0.16mg/L; however, in PA0009, it was possible to measure concentrations below this value and report these as a numeric result. The LLOQ in PA0008 will therefore be applied to the PA0009 data in order to retain consistency in reporting across the studies. Thus, numeric values of less than 0.16mg/L (<0.16mg/L) in PA0009 will be imputed with half the LLOQ from PA0008 (ie, 0.08mg/L) prior to summary reporting or any derivation of composite parameters. The original values will be included in the listing.

Any CRP values  $\geq 500$ mg/L will be set to missing prior to performing the MI procedure (Table 4–1) as these are considered to be extreme outliers.

CRP values at PA0008 Baseline and PA0009 EV will be taken from the PA0008 database (Baseline and Week 48 records respectively).

### 8.1.8 American College of Rheumatology Response Criteria

ACR20 response is defined as at least a 20% improvement (decrease) from PA0008 Baseline values for each of the following:

- TJC (based on 78 joints).
- SJC (based on 76 joints).
- At least 3 of the 5 remaining core set measures:
  - Disease activity as assessed by PGADA.
  - Disease activity as assessed by PhGADA.
  - Pain as assessed by PtAAP.
  - Physical function as assessed by the HAQ-DI.
  - Acute phase response as assessed by the CRP.

ACR response will be assessed using component assessments from the same analysis visit, ie, after applying any visit mapping as outlined in Section 3.5.

The following rules will be applied:

- For component scores with a Baseline value of 0, the percentage improvement is not calculable and will be considered as not having met the criteria for improvement at each visit. This will be applied and considered to be part of the OC analysis.
- In the case of partial data at a specific visit, if there are sufficient data to calculate a response eg, if results are available for TJC, SJC and at least 3 of the remaining core set assessments and these fulfil the criteria for percentage improvement (eg, 20% improvement for ACR20), this subject will be included in the summary of OC results as an ACR20 responder at the specific visit.
- Similarly, if there are sufficient data to calculate nonresponse regardless of missing data, this subject will be included in the summary of OC results as a nonresponder at the specific visit.
- For all non-missed visits, if it is not possible to determine response or nonresponse due to missing component scores, this subject will be excluded from the OC analysis at the specific visit, and regarded as a nonresponse in the NRI analysis.

Further details regarding these calculation algorithms and rules for handling missing components are provided in [Section 12.1](#).

ACR50 and ACR70 are defined similarly, using a 50% or 70% improvement from Baseline, respectively. An ACR70 responder at a given visit is therefore also an ACR50 and an ACR20 responder.

### 8.1.9 Body surface area affected by psoriasis

The BSA palm method will be used for the evaluation of BSA affected by psoriasis. The subject's hand, including the palm, fingers, and thumb, is used as the reference point for measuring how much of their skin is affected by psoriasis, representing roughly 1% of the body's surface. The full and regional BSA percentage affected will be calculated as multipliers of the percentage of the palm affected as follows:

- Head and neck=10% (10 palms)
- Upper extremities=20% (20 palms)
- Trunk=30% (30 palms)
- Lower extremities=40% (40 palms)
- Total BSA=100% (100 palms).

### 8.1.10 Psoriasis Area and Severity Index Response

The PASI is the most commonly used and validated assessment for grading the severity of psoriasis in clinical studies ([Feldman, 2004](#)). The PASI quantifies the severity and extent of the disease and weights these with the percentage of BSA involvement.

The body is divided into 4 sections as described in [Table 8-4](#). Each of these sections is scored by itself, and then the 4 scores are combined into the final PASI.

For each section, the percent of area of skin affected (A), is estimated and then transformed into a grade from 0 to 6:

- 0: 0% of area affected.

- 1: < 10% of area affected.
- 2: 10-<30% of area affected.
- 3: 30-<50% of area affected.
- 4: 50-<70% of area affected.
- 5: 70-<90% of area affected.
- 6: ≥90% of area affected.

**Table 8-4: Body areas for calculation of psoriasis area and severity index**

Body area	Details of area	BSA	Degree of involvement of body area a
Head (h)	Face, back of head	10%	0 to 6
Upper limbs (u)	Left, right, upper lower, flexor surface, extensor surface	20%	0 to 6
Trunk (t)	Front, back, groin	30%	0 to 6
Lower limbs (l)	Left, right, upper lower, flexor surface, extensor surface, including buttocks	40%	0 to 6
Total		100%	

BSA =- body surface area.

a Where 0=none; 1=1% to <10% affected, 2=10% to <30% affected, 3=30% to <50% affected, 4=50% to <70% affected, 5=70% to <90% affected, 6= ≥90% affected.

Within each body area, the severity is estimated by 3 clinical signs: redness (R), thickness (T), and scaliness (S) (each on a 5-point scale: 0=none, 1=slight, 2=moderate, 3=marked, and 4=very marked). The PASI is a measure of the average redness, thickness, and scaliness of the psoriatic skin lesions, multiplied by the involved psoriasis area score of the respective section, and weighted by the percentage person's skin for the respective section:

$$PASI = 0.1 * Ah * (Rh + Th + Sh) + 0.2 * Au * (Ru + Tu + Su) + 0.3 * At * (Rt + Tt + St) + 0.4 * Al * (Rl + Tl + Sl) \quad (13)$$

where

- Rh, Ru, Rt, and Rl is the redness score of plaques on the head, upper limbs, trunk, and lower limbs;
- Th, Tu, Tt, and Tl is the thickness score of plaques on the head, upper limbs, trunk, and lower limbs;

- Sh, Su, St, and Sl is the scaliness score of plaques on the head, upper limbs, trunk, and lower limbs;
- Ah, Au, At, and Al is the degree of involvement for the head, upper limbs, trunk, and lower limbs.

The PASI score ranges from 0 to 72 with a higher score indicating increased disease severity.

The following calculation rules will be applied:

- If 2 or fewer severity (redness, thickness, or scaliness) measurements are missing for a certain region, the average of the remaining non-missing assessments will be utilized to substitute the missing assessment(s).
- If the area of affected skin and/or all severity measurements for 2 or fewer body areas are missing, the missing (R+T+S) x A for a body area will be substituted by the average of the available (R+T+S) x A. Otherwise the PASI will be set to missing.

The percent improvement in PASI scores from PA0008 Baseline will be computed as follows:

$$\text{Percent improvement} = 100 * \frac{\text{baseline PASI} - \text{PASI}}{\text{baseline PASI}} \quad (14)$$

If a subject has experienced an improvement, this measure will be positive. If a subject has experienced a worsening in their condition, this measure will be negative.

The PASI75, PASI90, and PASI100 responses will be 1 if there was at least 75%, 90%, and 100% (respectively) improvement from PA0008 Baseline in the PASI score, and 0 if there was less than the cut-off value. A PASI100 responder at a given visit is therefore also a PASI90 and a PASI75 responder.

If BSA affected by psoriasis (determined by the BSA palm method described in [Section 8.1.9](#)) is <3% at PA0008 Baseline (or BSA at PA0008 Baseline is missing) then the PASI response will be set to missing.

Summaries of PASI responses will be restricted to subjects with a BSA affected by psoriasis of  $\geq 3\%$  at PA0008 Baseline.

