10.10 Psoriasis Area and Severity Index (PASI)

Psoriasis Area and Severity Index will be assessed in all subjects with study entry BSA affected by PSO $\geq 3\%$ at Baseline of PA0008 determined by the method described in Section 10.9 (ie, the BSA palm method).

The PASI is the most commonly used and validated assessment for grading the severity of PSO in clinical studies (Feldman, 2004). The PASI quantifies the severity and extent of the disease and weighs these with the percentage of BSA involvement.

The percent area of involvement (BSA%) is estimated across 4 body areas; head, upper limbs, trunk, and lower limbs and then transferred into a grade (Table 10–2).

The Investigator assesses the average redness, thickness, and scaliness of lesions in each body area (each on a 5-point scale); 0=none, 1=slight, 2=moderate, 3=marked, and 4=very marked.

The PASI score ranges from 0 to 72 with a higher score indicating increased disease severity.

Table 10–2: Body areas for calculation of percent BSA for PASI

Body area	Details of area	BSA	Degree of involvement of body area ^a
Head	Face, back of head	10%	0 to 6
Upper limbs	Left, right, upper lower, flexor surface, extensor surface	20%	0 to 6
Trunk	Front, back, groin	30%	0 to 6
Lower limbs	Left, right, upper lower, flexor surface, extensor surface, including buttocks	40%	0 to 6
Total		100%	

BSA=body surface area; PASI=Psoriasis Area and Severity Index

^a Where 0=none; 1=1% to <10% affected, 2=10% to <30% affected, 3=30% to <50% affected, 4=50% to <70% affected, 5=70% to <90% affected, 6=90% to 100% affected

The PASI75, PASI90, and PASI100 responses are based on at least 75%, 90%, and 100% improvement in the PASI score compared to Baseline in PA0008. Thereafter PASI will be analyzed for the purposes of determining response only in subjects with PSO involving at least 3% of BSA at Baseline of PA0008.

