### 4.2 Handling of missing data

#### 4.2.1 Handling of missing data for efficacy analysis

Calculation of derived efficacy variables in the presence of missing data is described in individual subsections of [Section 8.1](#). All derived efficacy variables will be calculated using observed data, and any resulting missing data will be handled as described in this section. All nonresponder imputation (NRI) and MI imputation as described below will be performed only for subjects in the FAS for PA0009.

Additional methods for deriving the PASI response in the presence of missing data are described in [Section 4.2.2](#).

For assessments missing during PA0008, which were to be used in PA0009 for reporting maintenance of response, the following approach will be used:

- For summaries of binary data following NRI, the imputed value from the PA0008 database will be used.
- For summaries of non-imputed (OC) data, the assessment will be left as missing.

For all visits in PA0009 (including PA0009 EV), missing values for binary secondary/other efficacy variables (ACR20, ACR50, ACR70, PASI75, PASI90, PASI100, MDA) or values, which cannot be constructed (eg, for ACR either tender joint count [TJC]/swollen joint count [SJC] are missing or >2 out of the 5 remaining core set measures are missing) will be imputed using NRI. For each visit, subjects with missing data or who have dropped out of the study will be counted as nonresponders. This includes any subjects with missing Baseline values. For PASI response, NRI will be implemented only for subjects with BSA  $\geq 3\%$  at PA0008 Baseline.

For missing continuous secondary/other efficacy variables an MI approach will be used. This will be performed for the following endpoints:

- TJC and SJC

- Psoriasis Area and Severity Index (PASI)
  - For PASI the MI model will be restricted to subjects with a BSA affected by psoriasis of  $\geq 3\%$  at PA0008 Baseline. Subjects with a BSA affected by psoriasis of  $< 3\%$  at PA0008 Baseline will be excluded prior to performing the procedure outlined below.
- Patient's Global Assessment of Disease Activity (PGADA)
- Physician's Global Assessment of Disease Activity (PhGADA)
- Patient's Assessments of Arthritis Pain (PtAAP)
- Health Assessment Questionnaire – Disability Index (HAQ-DI)
- CRP

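### If severity is left blank for a clear body area, the PASI rule in SAP 8.1.10 overwrites a product known to be 0, or sets the score to missing

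*SAP*

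**What the plan says.** Equation 13 in SAP 8.1.10 begins "PASI = 0.1 * Ah * (Rh + Th + Sh) + 0.2 * Au * (Ru + Tu + Su" and continues with weights 0.3 for the trunk and 0.4 for the lower limbs. Each body area therefore contributes its weight times A × (R+T+S). The lowest area grade is "0: 0% of area affected".

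Two missing-data rules follow. The first covers one or two missing signs: "If 2 or fewer severity (redness, thickness, or scaliness) measurements are missing for a certain region, the average of the remaining non-missing assessments" is used in their place. The second covers a whole area: "If the area of affected skin and/or all severity measurements for 2 or fewer body areas are missing, the missing (R+T+S) x A" for that area "will be substituted by the average of the available (R+T+S) x A. Otherwise the PASI will be set to missing".

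Protocol 10.10 describes the rating: "The Investigator assesses the average redness, thickness, and scaliness of lesions in each body area". Each sign has a five-point scale that starts at 0 for none. Neither document says how severity is entered when an area is 0% affected.

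Downstream, SAP 4.2.1 applies nonresponder imputation (NRI) to missing PASI responses in subjects with at least 3% BSA at PA0008 Baseline: "For each visit, subjects with missing data or who have dropped out of the study will be counted as nonresponders". SAP 8.1 takes Baseline derived values from the PA0008 database and applies these derivations to PA0009 data only.

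**The concern.** The second rule looks at whether severity is present but not at the area grade. If A is 0, the product is 0 whatever R, T and S would have been, so nothing is missing that matters. Because the signs are ratings of lesions, an assessor could reasonably leave them blank for an area with none. Read literally, the rule then gives one or two clear areas the average of the remaining areas, and sets PASI to missing when three or four areas are clear and blank. The mirror case, with the area grade missing but R, T and S all recorded as 0, is handled wrongly in the same way.

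At stake are PASI75 and PASI90 at Week 48, which are secondary endpoints, and PASI response at later visits. An inflated score would also enter the observed-case and multiple-imputation analyses as if it had been observed.

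**Working it through.** **1. Check of the formula.** The largest product is A = 6 times R+T+S = 12, or 72. In all four areas, 72 × (0.1 + 0.2 + 0.3 + 0.4) = 72. This agrees with the SAP: "The PASI score ranges from 0 to 72 with a higher score indicating increased disease severity".

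**2. Size of the error in the follow-up score.** Let the clear, blank areas have total weight w, and let every other area have product p.
- Correct PASI = p × (1 − w).
- As written, with one or two such areas: each blank takes the mean p, so PASI = p.
- Ratio = 1 / (1 − w).

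With p = 3 (for example A = 1 and R+T+S = 3):

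| Clear and blank | 1 − w | Correct | As written | Ratio |
|---|---|---|---|---|
| Head | 0.9 | 2.7 | 3.0 | 1.11 |
| Head, arms | 0.7 | 2.1 | 3.0 | 1.43 |
| Legs | 0.6 | 1.8 | 3.0 | 1.67 |
| Trunk, legs | 0.3 | 0.9 | 3.0 | 3.33 |
| Head, arms, trunk | 0.4 | 1.2 | missing | – |
| All four | 0 | 0 | missing | – |

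Unequal products behave similarly. Take head product 3, arms recorded as 0, trunk and legs clear and blank. The mean of the available products is (3 + 0)/2 = 1.5, so PASI is 0.3 + 0 + 0.45 + 0.6 = 1.35 against a correct 0.3. If every available product is 0, the substitute is 0 and the score is right. For a known zero, the substituted value is never below the true one.

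**3. Effect on response.** The Baseline values are assumptions, since the documents give none. Improvement = 100 × (Baseline − PASI)/Baseline.

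| Case | Baseline | Correct | As written | Lost |
|---|---|---|---|---|
| (a) Trunk, legs blank; product 4 on head, arms | 12 | 1.2, 90.0% | 4.0, 66.7% | PASI75, PASI90 |
| (b) Trunk, legs blank; product 3 on head, arms | 8 | 0.9, 88.75% | 3.0, 62.5% | PASI75 |
| (c) Legs blank; product 3 elsewhere | 8 | 1.8, 77.5% | 3.0, 62.5% | PASI75 |
| (d) As (c) | 12 | 1.8, 85.0% | 3.0, 75.0% | none |

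With all four areas clear and blank, the correct improvement is 100%. As written, PASI is missing and the subject is a nonresponder under NRI for PASI75, PASI90 and PASI100.

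**4. Baseline can push the other way.** Suppose PA0008 used the same rule, and a subject had legs clear and blank at Baseline with product 12 elsewhere. Correct Baseline is 12 × 0.6 = 7.2; the stored value would be 12. If follow-up is fully recorded, with product 4 on head, arms and trunk and 0 on the legs, PASI is 4 × 0.6 = 2.4. Correct improvement is (7.2 − 2.4)/7.2 = 66.7%; calculated improvement is (12 − 2.4)/12 = 80.0%. PASI75 is then wrongly gained.

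**The case against.** **Blank severity is a premise, not a documented fact.** The scale has a code for no sign, and the eCRF is not shown. If the form requires a 0, the rule does no harm. This stands, and it makes the point conditional.

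**A benign reading exists.** A product with a factor of 0 is arguably not missing, so a programmer might never substitute it. But the trigger names missing severity on its own. Two careful programmers could produce different secondary results from the same text.

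**Some examples might have had no PASI form at Week 48.** SAP 4.2.2 records that, before Protocol Amendment 3, PASI was determined only if BSA at that visit was at least 3%. With area grade 1 on head and arms only, BSA is below 1% + 2% = 3%. Amendment 3 is dated 11 December 2019 (SAP 1). SAP 8.5 says all subjects had completed Week 48 before the pandemic, which SAP 10.2.4 dates to 11 March 2020. Many Week 48 visits therefore probably fell under the old schedule, although no visit dates are given. This stands for case (b) with grade 1. It does not remove case (c), where BSA is below 1% + 2% + 3% = 6% and can reach 3%. Nor does it remove case (a) if the product of 4 is grade 2 with R+T+S = 2, where BSA is at least 1% + 2% = 3%.

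**SAP 4.2.2 already deals with clear subjects whose PASI is missing.** It counts BSA of 0% as response and adds a conditional carry-forward. Both are supplementary and act only when total PASI is missing. They leave the NRI result unchanged and never correct an inflated score.

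**MDA is largely protected.** SAP 8.1.11 accepts either PASI of at most 1 or BSA of at most 3. This stands.

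**The study is single-arm and descriptive, with safety as its primary objective.** No hypothesis test depends on PASI. This limits the consequence but does not make the score correct.

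**Conclusion.** The point holds conditionally. If severity is blank for an area graded 0%, SAP 8.1.10 as written replaces a known zero with the average of the other areas, or discards the score when three or four areas are involved. The follow-up PASI is then too high whenever an available area has a product above 0. With equal products elsewhere, the factor runs from 1.11 to 3.33. PASI75 and PASI90 can be misclassified at Week 48 and later visits.

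A reader might infer that cleared skin will be scored as diseased in this trial, or that the reported response rates are biased downward. The documents support neither. They do not show how severity is recorded on clear skin, so the number affected is unknown and may be zero. For a known-zero product the follow-up score errs only upward, but percent improvement also depends on a Baseline PASI derived under PA0008 rules that are not shown; step 4 gives a case in the opposite direction. A material effect on MDA is not supported either.

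The rule should still be corrected: it can give a mathematically wrong score for secondary endpoints, and the remedy is nearly free.

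**What to change.** In SAP 8.1.10, before the two substitution rules, add:

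> If the area grade A is 0, or if R, T and S are all recorded as 0, set (R+T+S) x A to 0 for that body area. Apply the substitution rules, and the count of missing body areas, only to areas whose product is not already determined.

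Also check that the PA0008 Baseline PASI was derived on the same basis, and state the result in the SAP. If it was not, percent improvement compares scores built under two conventions.

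The cost is a short SAP insertion, about one line of code, and a look at the PA0008 derivation. No new data are needed, and results do not change if the forms are complete.
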